7.5.5 GVHD-FREE SURVIVAL

GVHD-free survival is defined as being alive, free of active acute or chronic GVHD, free of any next-line GVHD therapy, and free of escalation of prednisone-equivalent steroid dose to 2.5mg/kg/day or more. The GVHD-free survival at Day 56 will be computed as a binary outcome. The proportion of patients in the ITT population with GVHD-free survival at Day 56 will be evaluated by the treatment arm. These proportions will be described by sample proportions and 95% Wilson score CIs. A logistic mixed model will be used to evaluate the effect of study treatment on Day 56 GVHD-free survival while accounting for center-group and MN risk, with center-group included as a random effect and treatment arm and MN risk as fixed effects. **Table 23** contains the estimand for GVHD-free survival. The clinical question of interest is: what is the difference in Day 56 GVHD-free survival between AAT combined with corticosteroids versus PTM combined with corticosteroids in patients with high risk acute GVHD following allogeneic HSCT, regardless of discontinuation of study treatment?

Table 23: Estimand for GVHD-free Survival

Estimand Attribute	Definition		
Variable	Day 56 GVHD-free Survival, refer to Sections 6.3.5 and 7.9 for details		
Treatment	AAT(+corticosteroids) or PTM (+corticosteroids), refer to Section 2.1 for details		
Population	Patients with high risk acute GVHD following allogeneic HSCT		
Intercurrent Events	Event	Strategy	Description
	1. Death before Day 56	Composite strategy	Classified as a failure
	2. Development of aGVHD or cGVHD before Day 56	Composite strategy	Classified as a failure
	2. Initiation of additional systemic aGVHD treatment ¹ before Day 56	Composite strategy	Classified as a failure
	3. Discontinuation of study therapy	Treatment policy	No effect on variable
Population-level Summary	Proportion of patients with GVHD-free at Day 56 with 95% CIs for each arm; adjusted odds ratio from logistic mixed model with 95% CI and p value		

¹ Includes next-line GVHD therapy and escalation of prednisone-equivalent steroid dose to 2.5mg/kg/day or more.

7.5.6 ACUTE GVHD RESPONSE TO AAT/PTM

The proportions of patients with CR, PR, and TF will be tabulated by treatment arm at Days 7, 14, 21, 28, and 56 for all patients in the ITT population and at Day 86 for the subset of patients that remained on study maintenance treatment after Day 28. Goodman simultaneous 95% CIs (Goodman 1965) will be provided for the response category proportions. These proportions will be compared between treatment arms using Fisher's exact test. If a patient does not complete the acute GVHD assessment on an evaluation day for any reason (e.g. missed visit, withdrawal from the study, loss to follow-up), they will be assigned as a TF on that Day. Moreover, patients who die, initiate either approved or unapproved next-line GVHD therapy, or have escalation of prednisone-equivalent steroid dose to 2.5mg/kg/day or more prior to an acute GVHD assessment will be classified as non-responders (NR) at the corresponding Day.

7.5.7 ACUTE GVHD RESPONSE ALLOWING FOR APPROVED NEXT-LINE THERAPY

The proportions of patients with CR, PR, and TF will be tabulated by treatment arm at Days 7, 14, 21, 28, and 56 for all patients in the ITT population and at Day 86 for the subset of patients that remained on study maintenance treatment after Day 28. Goodman simultaneous 95% CIs (Goodman 1965) will be provided for the response category proportions. These proportions will be compared between treatment arms using Fisher's exact test. If a patient does not complete the acute GVHD assessment on an evaluation day for any reason (e.g. missed visit, withdrawal from the study, loss to follow-up), they will be assigned as a TF on that Day. Moreover, patients who die, initiate next-line GVHD therapy that is not approved by the protocol chairs, or have escalation of prednisone-equivalent steroid dose to 2.5mg/kg/day or more prior to an acute GVHD assessment will be classified as non-responders (NR) at the corresponding Day.

The overall response (CR+PR) rate at Day 28 allowing for approved next-line treatments will be compared between treatment arms. A logistic mixed model will be used to evaluate the effect of study treatment on Day 28 overall response with adjustment for treatment center-group and MN risk category (high vs. standard), with center-group (defined in section 7.1) included as a random effect and treatment arm and MN risk as fixed effects. This analysis will use the ITT population. A two-sided Wald test of the treatment arm odds ratio in the logistic mixed model will be performed at a significance level of 5%. The standardized log odds ratio estimate from this model will be used as the test statistic (Z-statistic). The proportion of patients with an overall response at Day 28 will be described by treatment arm by sample proportions and 95% Wilson score CIs. Adjusted odds ratio estimates from the logistic mixed model of Day 28 overall response will be summarized in a regression table.

7.5.8 SYSTEMIC INFECTIONS

The frequency of Grade 2-3 infections occurring from randomization until 30 days post-last dose of AAT/PTM will be tabulated in the safety population by treatment arm, disease site, date of onset, and severity, with Grade defined per the BMT CTN Technical MOP.

The time from randomization until the first Grade 2-3 infection will be described graphically using the Aalen-Johansen estimator, with death before infection treated as a competing risk. Estimates of the cumulative incidence of Grade 2-3 infection will be provided at 3 months post-randomization along with 95% CIs computed using the complementary log-log transformation. Gray's test will be used to compare the cumulative incidence of Grade 2-3 infection within 3 months of randomization between arms.

7.5.9 ADVERSE EVENTS (AES)

The frequency of Grade 3-5 TEAEs per CTCAE version 5.0 occurring from randomization until 30 days post-last dose will be tabulated by the organ system for each treatment arm in the safety population.

The proportions of patients experiencing a Grade 3-5 TEAE will be described by arm using 95% Wilson score CIs and compared between treatment arms using Barnard's exact test.

7.5.10 CHRONIC GVHD

The time from randomization until the onset of chronic GVHD of any severity (mild, moderate, or severe per 2014 NIH Consensus Criteria) will be described in the ITT population graphically using the Aalen-Johansen estimator, with death prior to chronic GVHD onset treated as a competing risk. Estimates of the cumulative incidence of chronic GVHD will be provided at 6 and 12 months post-randomization along with 95% CIs computed using the complementary log-log transformation. Gray's test will be used to compare the cumulative incidence of chronic GVHD within 12 months of randomization between arms as the primary analysis.

In a supplementary analysis, a Cox proportional hazards model with mixed effects will be used to compare the cause-specific hazards of chronic GVHD between treatment arms while adjusting for an MN risk fixed effect and center-group lognormal frailties. The Cox regression model will be used to evaluate the adjusted hazard ratio of treatment (AAT vs. PTM) using a point estimate and a 95% CI.

The maximum severity of chronic GVHD through 12 months post-randomization will be tabulated by treatment arm.

7.5.11 RELAPSE/PROGRESSION OF PRIMARY DISEASE

The time from randomization until relapse/progression of the primary disease will be described in the ITT population graphically for each treatment arm using the Aalen-Johansen estimator, with death prior to relapse/progression treated as a competing risk. Estimates of the cumulative incidence of relapse/progression will be provided at 6 and 12 months post-randomization along with 95% CIs computed using the complementary log-

log transformation. Gray's test will be used to compare the cumulative incidence of relapse/progression within 12 months of randomization between arms as the primary analysis.

In a supplementary analysis, a Cox proportional hazards model with mixed effects will be used to compare the cause-specific hazards of relapse/progression between treatment arms while adjusting for an MN risk fixed effect and center-group lognormal frailties. The Cox regression model will be used to evaluate the adjusted hazard ratio of treatment (AAT vs. PTM) using a point estimate and a 95% CI.

7.6 ANALYSIS OF EXPLORATORY ENDPOINTS

7.6.1 SERUM AAT LEVELS

The pharmacokinetic parameters maximum concentration (Cmax) and trough concentration (Ctrough) for serum antigen AAT concentrations and serum functional AAT concentrations (AAT concentrations with functional activity) will be reported and summarized in the PK population at Days 0, 16, 28, and 56 post-treatment initiation by treatment arm using the n, mean, standard deviation (SD), coefficient of variation (CV%), median, range, geometric mean, and geometric CV%. Ctrough will also be summarized on Days 8 and 24.

7.6.2 STOOL AAT LEVELS

The stool concentration of AAT may be summarized at baseline and at Days 8 and 28 post-treatment initiation by treatment arm using the mean, median, quartiles, and range. The detailed analysis of this endpoint may be described in a separate document when data become available.

7.6.3 IMMUNE CELL SUBSETS

Peripheral blood ratios of T regulatory to T effector (Treg/Teff) cells and Natural Killer (NK) cell populations may be described by treatment arm using the sample mean, median, range, and quartiles at baseline and Days 16, 28, and 56 post-treatment initiation in tables of summary statistics and displayed graphically using box plots. Changes in levels from baseline to each subsequent assessment time may be described similarly in summary tables and compared between treatment arms using Wilcoxon rank sum tests. The detailed analysis of this endpoint may be described in a separate document when data become available.

7.6.4 INFLAMMATORY CYTOKINES AND GVHD BIOMARKERS

Serum levels of IL-1 β , IL-6, IL-10, TNF α , amphiregulin (AREG), heparin sulfate, ST2, and REG3 α may be described by treatment arm using the sample mean, median, range, and quartiles baseline and at Days 8, 28, and 56 post-treatment initiation in tables of summary statistics and displayed graphically using box plots. Changes in levels from baseline to each subsequent assessment time may be described similarly in summary tables and compared between treatment arms using Wilcoxon rank sum tests. The detailed analysis of this endpoint may be described in a separate document when data become available.

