5.8.3 Immune Subsets

The changes in peripheral blood ratios of T regulatory to T effector (Treg/Teff) cells, Natural Killer (NK) cells and other cellular immune subsets from baseline to Days 16, 28, and 56 post-treatment initiation will be summarized using descriptive statistics at each time point and compared between treatment groups using Mann-Whitney nonparametric tests. Select immune subsets may also be analyzed using a linear mixed model adjusting for baseline value, time and treatment, as well as a treatment by time interaction term.

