5.8.4 Inflammatory Cytokines and GVHD Biomarkers

Serum levels of inflammatory cytokines (e.g., IL-1 β , IL-6, IL-10, TNF α), damage associated molecular patterns (e.g., heparan sulfate) and select GVHD biomarkers (eg, ST2, REG3 α) at baseline and at Days 8, 28, and 56 post-treatment initiation will be summarized using descriptive statistics at each time point and compared between treatment groups using Mann-Whitney nonparametric tests. Select measurements may also be analyzed using a linear mixed model adjusting for baseline value, time, and treatment, as well as a treatment by time interaction term.

5.8.5 Overall and Organ-Specific Response Rates by Refined Minnesota Risk and Biomarker-Based Risk Classifications

The proportions of patients with an overall response (complete or partial) and response rate of each GVHD target organ at Day 28 post-randomization will be described by Refined Minnesota risk category (A vs B; see Section 2.4.1, #3) and by Ann Arbor biomarker risk score (1, 2, or 3) using sample proportions and confidence intervals and compared on each factor using the chi-square test or Fisher's exact test as appropriate.

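### The SAP names only Wilcoxon tests on raw change from baseline for cytokines, biomarkers and immune subsets; a stated log-scale, baseline-adjusted model would be more precise at almost no cost

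*SAP*

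**What the plan says.** **SAP.** Section 7.6.4 covers cytokines and GVHD biomarkers at baseline and Days 8, 28 and 56: "Changes in levels from baseline to each subsequent assessment time may be described similarly in summary tables and compared between treatment arms using Wilcoxon". Section 7.6.3 treats Treg/Teff and NK cells alike, with changes "compared between treatment arms using Wilcoxon rank sum tests". No transformation or baseline-adjusted model is named. Both sections then leave room: "The detailed analysis of this endpoint may be described in a separate document when data become available". SAP 7.1 tests exploratory endpoints at two-sided 1% and treats testing outside the hierarchy as descriptive.

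**Protocol.** In 5.8.4 the default for cytokines and biomarkers is a rank test on the level: values "will be summarized using descriptive statistics at each time point and compared between treatment groups using Mann-Whitney nonparametric tests". For immune subsets (5.8.3) the default is already a rank test on change. Both sections add an optional model: "Select measurements may also be analyzed using a linear mixed model adjusting for baseline value, time, and treatment", with a treatment-by-time term, and "Select immune subsets may also be analyzed using a linear mixed model adjusting for baseline value, time and treatment". Neither states a log transform.

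**Declared changes.** SAP 7.11 lists one departure from the protocol, the exploratory significance level moving from 5% to 1%.

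**The concern.** Baseline blood samples are required of every patient, yet the only named comparison uses them by subtraction. In a randomized comparison, subtraction fixes the baseline slope at 1; a regression estimates it. Where baseline predicts follow-up imperfectly, fixing the slope leaves avoidable noise in the comparison.

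These markers are the trial's direct look at the mechanism in protocol 1.6.5: enhanced Tregs and lower pro-inflammatory cytokines. With at most 68 per arm and a 1% level, a real pharmacodynamic effect could be missed for want of precision. The SAP already adjusts patient-reported outcomes for baseline score (7.6.8), so the method is not foreign to the plan.

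**Working it through.** **The plan's own figure.** No power is stated for these endpoints. The 86% stated for the primary endpoint reproduces: with 68 per arm, 50% against 75%, one-sided 2.5%, (0.25 − 1.96 × 0.0830)/0.0802 = 1.09, which gives 86.2%.

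**Inputs from the documents.** 68 per arm (protocol 5.2); two-sided 1% (SAP 7.1), critical value 2.576.

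**Assumed inputs.** Effect 0.5 SD; rho 0.3 to 0.7; equal variances at baseline and follow-up; log SD 1 for skewed markers. The documents give none of these.

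**Variance, in units of the level's variance**
- Change: 2(1 − rho) = 1.40, 1.00, 0.60 at rho 0.3, 0.5, 0.7.
- Baseline-adjusted: 1 − rho² = 0.91, 0.75, 0.51.
- Ratio: 2/(1 + rho) = 1.54, 1.33, 1.18.

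**Power by formula, normal data.** Power = Φ[0.5/(SD × √(2/n)) − 2.576], with n = 68 for the adjusted model and 68 × 0.955 for the rank test.
- Rho 0.3, change: Φ(2.408 − 2.576) = 43%. Adjusted: Φ(3.056 − 2.576) = 69%.
- Rho 0.5: 61% against 79%.
- Rho 0.7: 87% against 93%.

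**Simulation, 68 per arm.** Each cell is the Wilcoxon test on change against the baseline-adjusted model.

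| Setting | rho 0.3 | rho 0.5 | rho 0.7 |
|---|---|---|---|
| Same (normal) scale for both | 42% vs 66% | 59% vs 77% | 85% vs 92% |
| Skewed, marker falls: raw change vs log-scale model | 29% vs 65% | 39% vs 78% | 64% vs 94% |
| Skewed, marker rises: raw change vs log-scale model | 42% vs 65% | 56% vs 77% | 82% vs 93% |

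The first row is the like-for-like comparison, with power ratios 42/66 = 0.64, 59/77 = 0.77 and 85/92 = 0.92. The skewed rows combine two gains, baseline adjustment and the log scale. A rank ANCOVA on baseline keeps most of the gain, at 62% to 90% across these correlations.

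**When power is about halved.** On normal data by the formula, it takes rho near 0 (29% against 63%) to 0.2 (37% against 66%). For skewed falling markers it extends to rho 0.5 (39/78 = 0.50). For rising markers it does not occur in this range.

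**Fewer evaluable patients.** With 50 per arm, the formula ratios are 0.59, 0.72 and 0.87.

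**The log scale matters.** For skewed markers, the Wilcoxon test on raw change against an untransformed baseline-adjusted model gives 29% vs 38%, 38% vs 44% and 64% vs 58% at rho 0.3, 0.5 and 0.7. At 0.7 the planned test is the better of the two.

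**Levels to changes.** The protocol's default cytokine test on the level has 61% power by the formula (normal data) at any rho. The SAP's test on change has 43%, 61% and 87%. That switch costs power only below rho 0.5 and gains it above.

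**The case against.** A reader might infer that the SAP removed a committed analysis. It did not. The protocol's model was optional, for select measurements, beside a default rank test. For immune subsets SAP 7.6.3 reproduces that default. The SAP's own wording is permissive and allows a separate document, so the model is omitted rather than ruled out. All of this stands.

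A reader might also infer that power is halved in general, or that subtraction adds the whole baseline variance. The documents give no correlation, effect size or skewness to support the first. The second is true only at rho 0: at 0.5 change is no more variable than the level, and above 0.5 it is less variable. Nor do raw changes mainly track the starting value. With no treatment effect and log SD 1, their rank correlation with baseline is −0.54, −0.45 and −0.34 at rho 0.3, 0.5 and 0.7, and with follow-up +0.54, +0.45 and +0.35.

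Finally, a rank test is robust, holds its level, and avoids a rule for values below quantification. That is a fair preference, but a rank ANCOVA is robust too and keeps most of the precision.

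**Conclusion.** The point holds as a low-cost improvement to an exploratory analysis. The named test is valid, so nothing here threatens the trial's main conclusion. It is less efficient than baseline adjustment whenever rho is below 1 on a normal scale. At 68 per arm, two-sided 1% and an assumed 0.5 SD effect, the like-for-like loss is about 24 points of power at rho 0.3, 18 at 0.5 and 7 at 0.7. A loss near half needs low correlation, or strong right skew in a falling marker judged against a log-scale model.

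The documentation point needs no assumption about the data. For cytokines and biomarkers the protocol compares levels and the SAP compares changes, yet SAP 7.11 declares only the change of significance level. The optional model is also left out without comment.

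**What to change.** In SAP 7.6.3 and 7.6.4, or in the separate biomarker document if it is finalised before unblinded marker data are seen:

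1. Make the between-arm comparison a linear mixed model on log-transformed post-baseline values, with log baseline, visit, treatment and treatment-by-visit. Report geometric mean ratios with confidence intervals at each visit.
2. State the log transform explicitly, since protocol 5.8.3 and 5.8.4 do not and the raw-scale model can do worse than the planned test.
3. Where many values are below quantification, use a rank ANCOVA on baseline.
4. Keep the change-from-baseline tables and box plots as description.
5. List in SAP 7.11 the omitted model and, for cytokines and biomarkers, the move from comparing levels to comparing changes.

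No new data are needed, and SAP section 1 permits revision before the database hard lock. The one real cost is a prespecified rule for values below quantification.

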7.6.5 OVERALL AND ORGAN-SPECIFIC RESPONSE RATES BY GVHD AND BIOMARKERS BASED RISK CLASSIFICATIONS

The proportions of patients with an overall response (complete or partial) and the response rate of each GVHD target organ at Day 28 will be described in the ITT population by MN risk (high vs. standard) and by Ann Arbor biomarker risk score (1, 2, or 3) using sample proportions and 95% Wilson score CIs and compared on each factor using Fisher's exact test.

In addition, a subgroup analysis of overall response by treatment arm will be conducted. Response rates for each arm within levels of MN risk and Ann Arbor biomarker score will be described using sample proportions and 95% Clopper-Pearson CIs. Potential differential treatment effects between subgroups will be evaluated using logistic regression models with treatment arm, risk classification, and an interaction of the two included as effects. Wald test p-values of the interaction terms will be reported to assess the presence of differential effects across subgroups. The results from the analysis by Ann Arbor biomarker risk score may be presented in a separate report depending on the biomarker data availability.

7.6.6 SYSTEMIC CORTICOSTEROID DOSE

The prednisone-equivalent corticosteroid dose being administered (measured in prednisone equivalent) will be described at baseline, at Days 7, 14, 21, 28, 56, and 86 and at 6 and 12 months post-randomization by treatment arm in the ITT population using the sample mean, median, range, and quartiles in a table of summary statistics and displayed graphically using box plots. Changes in levels from baseline to each subsequent assessment time will be described similarly in summary tables and compared between treatment arms using Wilcoxon rank sum tests.

7.6.7 CMV REACTIVATION

Among patients who were CMV positive at transplant, the cumulative incidence of initiation of systemic treatment for CMV reactivation will be described in the safety population graphically using the Aalen-Johansen estimator, with death treated as a competing risk. Estimates of the cumulative incidence of CMV reactivation will be provided at Day 56 for each arm along with 95% CIs computed using the complementary log-log transformation. Gray's test will be used to compare the cumulative incidence of CMV reactivation within 56 days post-randomization between arms.

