2.3.3 Exploratory Objectives

1. AAT levels in serum at Days 0, 8, 16, 24, 28, and 56 post-treatment initiation.
2. Stool concentrations of AAT at baseline and at Days 8 and 28 post-treatment initiation.

3. Blood ratios of T regulatory to T effector cells (Treg/Teff), Natural Killer (NK) cells and cellular immune subsets at baseline and at Days 16, 28, and 56 post-treatment initiation.
4. Serum levels of inflammatory cytokines and biomarkers at baseline and at Days 8, 28 and 56 post-treatment initiation.
5. Overall and organ-specific response rates comparison based on Minnesota (MN) risk groups (Revised Minnesota High vs Standard) and organ-specific response rates comparison based on biomarker-based risk groups.
6. Corticosteroid dose at baseline, Days 7, 14, 21, 28, 56, 86, 6 months and 12 months post-randomization.
7. CMV reactivation requiring therapy by Day 56 post-randomization.
8. Change in patient-reported outcomes from baseline to Day 28, Day 56, and 6-months post-randomization.
 - a. MD Anderson Symptom Inventory (MDASI)
 - b. Patient-Reported Outcome Measurements Information System (PROMIS)

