3.3.7 CMV-Reactivation

The proportion of patients requiring new systemic treatment for an increasing CMV PCR level per institutional practice for CMV-reactivation will be evaluated at Day 56 post-randomization. Patients receiving only standard of care viral prophylaxis will not be included in this assessment.

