5.5.3 General Analysis Guidelines

Primary analyses for the primary, secondary, and exploratory endpoints will use the primary analysis population except when otherwise specified. Analyses of each endpoint in each population will follow the analysis plans as described below in Sections 5.6, 5.7, and 5.8. We expect minimal missing data (< 5%) for the primary endpoint and secondary endpoints based on the past experience with a large phase III aGVHD treatment trial (BMT CTN protocol #0802. All secondary and exploratory analyses will use a two-sided significance level of 5%.

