5.8.7 CMV-Reactivation

The proportions of patients requiring new systemic treatment for CMV-reactivation by Day 56 post-randomization will be compared between the treatment groups using a chi-square test or Fisher's exact test as appropriate.

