6.4.7 CMV REACTIVATION

Cytomegalovirus (CMV) reactivations to be assessed include those requiring new systemic treatment for a CMV PCR level per institutional practice (patients receiving only standard of care viral prophylaxis will not be included in this assessment). Death prior to CMV reactivation will be treated as a competing risk. CMV reactivation time is defined as the time from the date of randomization until the documented date of CMV reactivation or death from any cause, whichever happens first. All CMV reactivations and deaths occurring on or after the randomization date will be included. Patients who are alive and free of CMV reactivation at the time of analysis will be censored at the last day known to be alive or at the analysis data freeze date, whichever is earlier. Patients experiencing event(s) after the analysis cut-off date will be censored at the analysis cut-off date.

Table 13: CMV Reactivation Competing Risks Definition

Situation	Date of Event or Censoring	Outcome
CMV reactivation occurred before or on analysis cutoff date	Date of CMV reactivation	CMV reactivation
Death without prior CMV reactivation occurred before or on analysis cutoff date	Date of death	Death
Death and/or CMV reactivation occurred, all events happened after analysis cutoff date	Analysis cutoff date	Censored
No death or CMV reactivation occurred, last known date alive is before or on analysis cutoff date	Last known date alive	Censored
No death or CMV reactivation occurred, last known date alive is after analysis cutoff date	Analysis cutoff date	Censored

Time of CMV reactivation = Date of Event or Censoring – Date of Randomization + 1

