7.11 CHANGES TO PROTOCOL-SPECIFIED ANALYSIS

The current SAP elaborates on the protocol-specified analysis. The sole change in the SAP from the protocol-specified analysis is that the significance level of the two-sided testing of exploratory endpoints is planned to change from 5% to 1%. Any future revisions to the SAP that constitute changes from the protocol-specified analysis, and the justification for these changes, will be documented here.

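### SAP 7.6.7 limits the Day 56 CMV-treatment analysis to an undefined CMV-positive subset; the protocol and SAP 6.4.7 set no such limit, and SAP 7.11 does not list it as a change

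*SAP*

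**What the plan says.** The protocol states the endpoint three times, each time without a condition on CMV status:

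- Objective (Protocol 2.3.3): "CMV reactivation requiring therapy by Day 56 post-randomization".
- Endpoint (Protocol 3.3.7): "The proportion of patients requiring new systemic treatment for an increasing CMV PCR level per institutional practice", evaluated at Day 56. One group is set aside: "Patients receiving only standard of care viral prophylaxis will not be included in this assessment".
- Analysis (Protocol 5.8.7): "The proportions of patients requiring new systemic treatment for CMV-reactivation by Day 56 post-randomization will be compared between the treatment groups", by chi-square or Fisher's exact test.

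The default population comes from Protocol 5.5.3: "Primary analyses for the primary, secondary, and exploratory endpoints will use the primary analysis population except when otherwise specified". That population is all randomised patients.

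SAP 6.4.7 keeps the event and the prophylaxis exception and adds death as a competing risk. It again sets no CMV-status condition: "Patients who are alive and free of CMV reactivation at the time of analysis will be censored".

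SAP 7.6.7 then says: "Among patients who were CMV positive at transplant, the cumulative incidence of initiation of systemic treatment for CMV reactivation will be described". The analysis uses the safety population, with a cumulative incidence at Day 56 and Gray's test between arms.

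On departures from the protocol, SAP 7.11 says: "The sole change in the SAP from the protocol-specified analysis is that the significance level of the two-sided testing of exploratory endpoints" moves from 5% to 1%.

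**The concern.** The section that defines the CMV endpoint and the section that analyses it describe different sets of patients. A programmer who follows SAP 7.6.7 will report a quantity that neither the protocol nor SAP 6.4.7 defines, and a reader of SAP 7.11 would not know it.

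The endpoint describes infection risk when an immunomodulator is added to high-dose steroids. Protocol 1.6.6 also names CMV infection among the most common adverse events in the phase 3 trial of ruxolitinib, the recommended next-line drug. A planned look at CMV treatment that leaves out part of the treated sample is less complete than the protocol promised, and its rate cannot be read as the protocol's proportion of patients.

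The subset itself is also unclear. The SAP does not say whether positivity refers to recipient, donor or either, or whether it is judged by serology or PCR. CMV status is not among the baseline variables in SAP 7.2.1. Two programmers could build different denominators.

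**Working it through.** **Step 1: set the sections side by side.**

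| Place | Who is analysed | CMV-status condition | Method |
|---|---|---|---|
| Protocol 3.3.7, 5.8.7 (population from 5.5.3) | All randomised by default, less prophylaxis-only patients | None | Proportion by Day 56; chi-square or Fisher |
| SAP 6.4.7 | Not stated; prophylaxis-only patients set aside | None | Time to event, death competing |
| SAP Table 14 | ITT for exploratory endpoints; safety population for safety endpoints | None | Not given |
| SAP 7.6.7 | Safety population | Positive at transplant only | Day 56 cumulative incidence; Gray's test |
| SAP 7.11 | No change listed | No change listed | No change listed |

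SAP 7.6.7 differs from the protocol in three ways: the CMV-status restriction, the safety population in place of the ITT default, and Gray's test in place of chi-square or Fisher. SAP 7.11 lists none of them. With no censoring before Day 56, the cumulative incidence with death as a competing risk equals the simple proportion. So the restriction, rather than the change of estimator, is what makes the reported rate a different quantity.

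**Step 2: follow a treated patient outside the subset.** Suppose such a patient starts pre-emptive CMV therapy, which the protocol's supportive care guidelines expect after a positive assay.

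- SAP 7.6.7: not counted.
- SAP 7.5.8: compares the first Grade 2-3 infection between arms, with no CMV-status condition. In Protocol Appendix G, viremia that falls by at least two-thirds after 2 weeks of therapy is Grade 1, so this patient is not counted. Clinically active CMV, or viremia that does not fall that far, is Grade 2, and end-organ disease is Grade 3. Those events do enter, but inside a composite of all infections and only as a patient's first such infection. (This assumes that the manual SAP 7.5.8 cites for grading matches Appendix G.)
- Adverse event tables: infections need not be reported as an AE or SAE (Protocol 4.4.1, SAP 6.5), so these tables need not show the event.

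Treated viremia that responds can therefore be absent from every planned between-arm comparison.

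**Step 3: illustrate the size.** The documents give no CMV-positive share, no CMV treatment rate and no power for this endpoint, so there is no stated figure to reproduce. The inputs below are assumptions, apart from the planned 136 patients (Protocol 5.1), all taken as dosed and with the prophylaxis exception ignored.

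- Share CMV-positive s: 0.5 to 0.7
- Day 56 treatment rate if positive, r₊: 0.30 to 0.40
- Day 56 treatment rate otherwise, r₋: 0.05 to 0.10

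Formulas:

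- All-patient rate = s·r₊ + (1−s)·r₋
- Shift = r₊ − all-patient rate = (1−s)(r₊ − r₋)
- Events left out = 136(1−s)·r₋
- Their share of all events = (1−s)·r₋ ÷ all-patient rate

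| s | r₊ | r₋ | All-patient rate | Shift (points) | Events left out | Share of events |
|---|---|---|---|---|---|---|
| 0.5 | 0.30 | 0.05 | 17.5% | 12.5 | 3.4 | 14.3% |
| 0.5 | 0.30 | 0.10 | 20.0% | 10.0 | 6.8 | 25.0% |
| 0.5 | 0.40 | 0.05 | 22.5% | 17.5 | 3.4 | 11.1% |
| 0.5 | 0.40 | 0.10 | 25.0% | 15.0 | 6.8 | 20.0% |
| 0.7 | 0.30 | 0.05 | 22.5% | 7.5 | 2.0 | 6.7% |
| 0.7 | 0.30 | 0.10 | 24.0% | 6.0 | 4.1 | 12.5% |
| 0.7 | 0.40 | 0.05 | 29.5% | 10.5 | 2.0 | 5.1% |
| 0.7 | 0.40 | 0.10 | 31.0% | 9.0 | 4.1 | 9.7% |

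Patients left out: 136 × 0.5 = 68 down to 136 × 0.3 ≈ 41. The shift is zero if everyone is positive or the two rates are equal.

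**The case against.** The strongest defence is the word reactivation, which ordinarily presupposes earlier infection. On that reading SAP 7.6.7 only makes the at-risk set explicit. This is a reasonable clinical position, and it leaves open whether a first, donor-derived infection in a CMV-negative recipient counts. A reader might infer that such an infection is plainly an event under the protocol; the documents do not settle that. What they do settle is that the event is defined by starting new systemic treatment, with no status condition, and that the SAP neither gives the at-risk argument nor discloses the restriction.

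A reader might also infer that the restriction biases the comparison of AAT with placebo. It does not. Status at transplant is fixed before randomisation, so the arms remain comparable within the subset. For the same reason, expressing the shift in standard errors of a rate would say nothing about the treatment contrast.

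Nor is it right that CMV in the other patients is never compared: Grade 2-3 events reach SAP 7.5.8. What is missing is a CMV-specific comparison, and any comparison at all of treated viremia that responds.

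Use of the safety population is defensible. Protocol 5.5.2 assigns safety data to patients as treated, and 5.5.3 allows exceptions to the default. It is nevertheless a change that SAP 7.11 should list.

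Finally, the endpoint is exploratory, tested at 1%, and outside the testing hierarchy, so SAP 7.1 treats it as descriptive.

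**Conclusion.** The point stands as an undisclosed mismatch between definition and analysis. SAP 7.6.7 reports the CMV-treatment rate in a subset it does not define, and the statement in SAP 7.11 that there is only one change is incorrect. The consequences are incomplete coverage of CMV treatment and a rate that answers a narrower question than the protocol's. The primary result, the hierarchy and the mortality monitoring are untouched.

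The size cannot be fixed from the documents. The 6 to 17.5 points, and the roughly 2 to 7 events left out (5% to 25% of all events), hold only under the assumed shares and rates. The mismatch in the text depends on none of those assumptions.

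**What to change.** - In SAP 7.6.7, run the Day 56 cumulative incidence and Gray's test in the whole safety population regardless of CMV status, keeping the prophylaxis exception in SAP 6.4.7.
- Report patients CMV-positive at transplant as a labelled subgroup alongside it. Define the term: recipient, donor or either, and by which test.
- In SAP 7.11, list the changes from the protocol that remain: the safety population instead of the ITT default, and Gray's test instead of chi-square or Fisher.

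The cost is SAP wording and one extra table. The team should confirm that the start of CMV treatment is recorded for all treated patients. Infection reporting runs from enrolment through 3 months for everyone (Protocol Table 4-1), but the documents do not show a form that captures treatment start.
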